3.2. Ipilimumab monotherapy in advanced melanoma

Ipilimumab is a fully humanized IgG1 monoclonal antibody (mAb) binding to the anti-cytotoxic T-cell lymphoma-4 antigen (CTLA-4). Ipilimumab is an approved therapy for patients with metastatic melanoma (Yervoy® Prescribing Information, 2018) and has demonstrated improved overall survival as monotherapy and in combination with dacarbazine [19, 20].

In melanoma, the completed Phase 3 study MDX010-20 demonstrated a clinically meaningful and statistically significant survival benefit with ipilimumab in pre-treated advanced melanoma [19]. The study compared the OS of ipilimumab plus a melanoma-specific vaccine (gp100) to that of gp100 alone. A second comparison defined the OS of ipilimumab alone vs gp100 alone. Both comparisons demonstrated statistically significant improvements in OS ($P = 0.0004$ and 0.0026 , respectively). The 1-year survival for the two ipilimumab-containing groups, respectively, was 44% and 46% respectively, compared to 25% for the gp100 control group. The 2-year survival was 22%, 24% and 14% respectively. The median survival was 10, 10.1, and 6.4 months, for ipilimumab plus gp100, ipilimumab monotherapy, and gp100 monotherapy, respectively.

Ipilimumab has been shown to produce prolonged survival in over 20% of patients based on long-term follow up on a composite analysis of 12 clinical studies with ipilimumab in advanced melanoma [21]. In this series, 1,257 patients were pretreated and 604 were previously untreated for metastatic disease. The dose of ipilimumab was 3 mg/kg for 965 patients and 10 mg/kg for 706 patients. The median overall survival for the whole patient population was 11.4 months. Most importantly, the survival curve reached a plateau of 22% at 3 years, which extended to 10 years, and it was independent of the dose.

Both the KEYNOTE 006 and CheckMate 067 studies have demonstrated superior efficacy with anti-PD1 therapy (pembrolizumab and nivolumab) over ipilimumab [1, 17]. Hazard ratios for PFS and OS in treatment naïve patients with anti-PD-1 versus ipilimumab were reported to be 0.54-0.55 and 0.65- 0.73, respectively (all statistically significant with $P < 0.05$). Based on this data, ipilimumab is now considered a second/third line agent or used in combination with anti-PD-1 therapy (see Nivolumab/Ipilimumab section 3.3).

Most common adverse reactions ($\geq 5\%$) with ipilimumab as a single agent are fatigue, diarrhea, pruritus, rash, and colitis [YERVOY package insert, 2018]. These usually are immune-related toxicities based on the mechanism of action for anti-CTLA-4 therapy. Refer to package insert for further information on adverse reactions. Severe grade 3-4 adverse events (treatment related) have been reported in 23-28% patients receiving ipilimumab at 3mg/kg [1, 19]. See Table 3-1.

3.3 Nivolumab plus Ipilimumab

Combination therapy has emerged as an effective treatment option for advanced melanoma. The efficacy data further support the combination of nivolumab plus ipilimumab as first-line treatment option for patients with advanced melanoma, regardless of BRAF mutation status, based on the results of the CheckMate 069 and 067 studies [1, 22]. The combination of these immune checkpoint inhibitors was approved for the treatment of unresectable or metastatic melanoma in the USA in January 2016 and in the European Union in May 2016.

In a Phase 2 trial of treatment-naïve patients with BRAF wild-type melanoma (CheckMate 069), 142 patients with previously untreated advanced melanoma were randomized in a 2:1 ratio to either receive both ipilimumab (3mg/kg) and nivolumab (1mg/kg) every 3 weeks followed by nivolumab (3mg/kg), or ipilimumab (3mg/kg) and placebo every 3 weeks followed by placebo every 2 weeks [22]. The combination of nivolumab and ipilimumab demonstrated a statistically significant improvement in ORR and longer PFS compared with ipilimumab alone with an ORR

of 61% (44/72) in patients treated with the combination versus 11% (4/37) in ipilimumab monotherapy. Complete responses were reported in 22% (16/72) in the combination group, and no patients in the ipilimumab monotherapy group. With a minimum follow-up period of 11 months, median PFS and median duration of response were not reached in the combination group, compared with mPFS of 4.4 months with ipilimumab monotherapy.

In CheckMate 067 study, 945 patients with previously untreated advanced or metastatic melanoma were randomized in a 1:1:1 ratio to receive nivolumab monotherapy, nivolumab (1mg/kg) and ipilimumab (3mg/kg) combination therapy, or ipilimumab monotherapy [1]. The study was primarily powered to demonstrate efficacy differences between nivolumab versus ipilimumab and nivolumab/ipilimumab versus ipilimumab. The observed ORRs were 43.7% in nivolumab monotherapy, 57.6% in the combination group, and 19% in ipilimumab monotherapy. Nivolumab/ipilimumab as well as nivolumab monotherapy demonstrated superior PFS and OS compared to ipilimumab monotherapy. The 12 month PFS rate was 42% and 49% in the nivolumab monotherapy and nivolumab/ipilimumab combination groups, respectively. Longer follow up showed the 3 year PFS rates were 32% and 39%, respectively. Similarly, the overall survival at 3 years was numerically higher with nivolumab/ipilimumab versus nivolumab alone (58% versus 52%).

While response rates are greater with nivolumab/ipilimumab combination therapy, the serious adverse event rates are also greater compared to monotherapies. In the CheckMate 067 study, 59% of patients experienced a grade 3-4 treatment related adverse event with nivolumab/ipilimumab (see Table 3-1) [1]. The more concerning grade 3-4 events included diarrhea/colitis and increased transaminase levels/hepatitis, seen in up to 9% of patients each. To address this issue, alternative dosing for anti-PD-1/anti-CTLA-4 combination therapy in advanced melanoma has been investigated. The randomized, double blinded phase 3b/4 CheckMate 511 study compared the standard nivolumab 1mg/kg plus ipilimumab 3mg/kg (nivo1/ipi3) dose levels to the inverse nivolumab 3mg/kg plus ipilimumab 1mg/kg (nivo3/ipi1) dose levels in patients with advanced melanoma [23]. Patients in both arms then continued on with maintenance nivolumab 480mg every 4 weeks if tolerating with disease control. The primary endpoint of safety showed a significant reduction in treatment related grade 3-4 adverse events with nivo3/ipi1 versus nivo1/ipi3 (34% versus 48%, P=0.0059). Efficacy was similar in both group but still early in follow up. The 12 month PFS rate was 46-47% between the two groups. A separate study (KEYNOTE 029) supports the use of lower dose ipilimumab in combination with anti-PD-1 therapy [24]. In this study of 110 patients with advanced melanoma treated with pembrolizumab 2mg/kg plus ipilimumab 1mg/kg, the treatment related grade 3-4 adverse event rate was 45% (immune-related grade 3-4 was 27%).

3.4 Cabozantinib

Cabozantinib (also known as XL184) is an oral tyrosine kinase inhibitor that targets VEGFR2, c-MET, AXL, and other RTKs with half maximal inhibitory concentration (IC₅₀) in the low nanomolar range [25]. Clinical activity with cabozantinib has been demonstrated in a range of tumor types, including advanced hepatocellular carcinoma, renal cell carcinoma and medullary thyroid cancer where the drug is now FDA approved [26-30]. The predicted terminal half life of cabozantinib at the approved dose of 60mg daily in RCC patients was 99hrs [Investigator's

Brochure version 14]. Of note, different pharmacokinetics was observed in medullary thyroid cancer patients. Cabozantinib is also highly protein bound in human plasma ($\geq 99.7\%$).

Cabozantinib has previously been studied in melanoma patients as cohort in a larger phase 2 randomized discontinuation trial (RDT) [9]. A total of 77 patients with advanced melanoma (62% cutaneous melanoma) were treated with cabozantinib at 100mg daily for a 12 week lead in period. Patients with stable disease after 12 weeks were randomized to either continue on cabozantinib or discontinue and evaluate for progression free survival (those patients with partial or complete responses would stay on drug). At week 12, the ORR was 5%; however 55% of patients with evaluable disease demonstrated some tumor regression (refer to Figure 3-1). Of the 26 patients with stable disease and randomized to stay on treatment or discontinue, the median PFS was 4.1 months versus 2.8 months (HR 0.59, P=0.284). The median overall survival of the entire cohort was 9.4 months.

[figure not shown]

Figure 3-1. Best change in tumor response (RECIST) at week 12 from baseline on the Phase 2 RDT of cabozantinib in patients with advanced melanoma. N=64 for evaluable patients.

The most common adverse events ($\geq 25\%$) reported for cabozantinib are diarrhea, fatigue, nausea, decreased appetite, palmar-plantar erythrodysesthesia syndrome (PPES), hypertension, vomiting, weight decreased, and constipation (Cabozantinib package insert, 2018). At the continuous 60mg daily dosing of cabozantinib in patients with advanced RCC, the treatment emergent grade 3-4 adverse event rate was 68% [27]. Dose reductions occurred in 60% of patients and drug discontinuation due to adverse event occurred in 9% of patients. In the phase 2 RDT of cabozantinib (100mg daily) in patients with advanced melanoma, safety data was reported on the 12 week lead in period [9]. During this window, dose reduction occurred in 29% of patients and drug discontinuation due to adverse event occurred in 8% of patients. The most common treatment emergent grade 3-4 events were fatigue (14%), hypertension (10%), and abdominal pain (8%) (see Table 3-2).

Table 3-2. Most frequently reported adverse events during the lead in stage regardless of causality on the phase II RDT of cabozantinib in patients with advanced melanoma.

	All grades (N = 77)	Grade $\geq 3^a$ (N = 77)
AE ^b	n (%)	n (%)
Fatigue	46 (60)	11 (14)
Diarrhoea	44 (57)	2 (3)
Nausea	39 (51)	1 (1)
Decreased appetite	35 (45)	0 (0)
Abdominal pain	24 (31)	6 (8)
Vomiting	23 (30)	2 (3)
Hypertension	22 (29)	8 (10)
Constipation	20 (26)	3 (4)
Dysgeusia	20 (26)	0 (0)
Hand-foot syndrome	19 (25)	4 (5)
Stomatitis	19 (25)	0 (0)
Aspartate aminotransferase increased	17 (22)	2 (3)
Dry mouth	17 (22)	0 (0)
Dysphonia	17 (22)	0 (0)
Rash	16 (21)	0 (0)
Weight decreased	16 (21)	0 (0)
Dyspnoea	13 (17)	3 (4)
Mucosal inflammation	13 (17)	0 (0)
Alanine aminotransferase increased	12 (16)	2 (3)
Hypomagnesaemia	12 (16)	0 (0)
Asthenia	11 (14)	4 (5)
Abdominal pain upper	11 (14)	1 (1)
Dizziness	11 (14)	1 (1)
Oral pain	11 (14)	1 (1)
Urinary tract infection	11 (14)	0 (0)
Back pain	10 (13)	4 (5)
Hypokalaemia	10 (13)	4 (5)
Pain in extremity	10 (13)	3 (4)
Dry skin	10 (13)	0 (0)

3.5 Nivolumab/Ipilimumab plus Cabozantinib

The triple combination of nivolumab/ipilimumab plus cabozantinib has been evaluated in a metastatic urothelial cancer and other genitourinary malignancies (non-clear cell RCC) [12]. In this phase 1 study, nivolumab/ipilimumab plus cabozantinib was studied in part 2, after nivolumab plus cabozantinib was cleared. Primary endpoint was to define maximum tolerated dose and the recommended phase 2 dose. Three dose levels of the triple combination were planned: cohort 5 – cabozantinib 40mg PO daily + nivo1/ipi1, cohort 6 - cabozantinib 40mg PO daily + nivo3/ipi1, and cohort 7 – cabozantinib 60mg PO daily + nivo3/ipi1. Data was presented on 18 subjects with a median follow up of 12.8 months. All grade adverse events were seen in 16/18 subjects (89%) and grade 3-4 adverse events were seen in 13/18 subjects (72%) (this was similar to the adverse event data for nivolumab/cabozantinib). Treatment related adverse events leading to drug discontinuation occurred in 2/18 (11.1%) during the maintenance phase with

nivolumab plus cabozantinib (colitis and hepatitis). Dose holds for nivolumab and cabozantinib occurred in 7/18 (39%) and 12/18 (67%) of subjects, respectively. Cabozantinib was dose reduced in 6/18 (33%) of subjects. Treatment related grade 3-4 adverse events occurring in 2 or more patients included fatigue, hypertension, lymphopenia, hypophosphatemia, hyponatremia, elevated ALT level, and elevated lipase level. Only 1 case each of grade 3-4 immune colitis and hepatitis were reported. Refer to tables 3-3 and 3-4 for adverse event summaries for the triple combinations. Of the 18 subjects treated with nivolumab/ipilimumab plus cabozantinib, 4 (22%) demonstrated an objective response, which included patients with advanced/metastatic penile cancer (n=1), sarcomatoid RCC (n=1), and urothelial carcinoma of the bladder (n=2). The recommended phase 2 dose was cabozantinib 40mg PO daily plus nivolumab 3mg/kg and ipilimumab 1mg/kg.

Table 3-3. Select clinical treatment related adverse events: any grade \geq 20% of patients and any irAE from the phase 1 study of Cabozantinib plus Nivolumab/Ipilimumab.

Event	Cabozantinib-Nivolumab-ipilimumab (n=18) *	
	Any Grade	G3-G4
n (%)		
Fatigue	15 (83)	2 (11)
Nausea or vomiting	12 (67)	-
Diarrhea	15 (83)	1(5)
Skin disorders (pruritus or dry skin or rash)	14 (78)	-
Anorexia	10 (55)	1(5)
Oral Mucositis or sore throat	8 (44)	1(5)
Hoarseness	8 (44)	-
Arthralgia and myalgia	8 (44)	-
Palmar-plantar erythrodysesthesia	4 (22)	-
Weight loss	7 (39)	-
Abdominal pain	3 (17)	-
Hypertension	3 (17)	3 (17)
Thromboembolic events	1(5)	1(5)
Infection (pyelonephritis)	-	-
irAE		
Colitis	1 (5) *	1 (5)*
Aseptic meningitis	-	-
Hypogonadism	-	-
Pneumonitis	2 (11)*	-
Hepatitis	1 (5) *	1 (5)*

Table 3-4. Laboratory abnormalities: any grade \geq 20% of patients and any irAE from the phase 1 study of Cabozantinib plus Nivolumab/Ipilimumab.

Events	Cabozantinib-nivolumab-ipilimumab (n=18)	
	Any Grade	G3-G4
n (%)		
Hematology		
Anemia	9(50)	-
Neutrophil count decreased	3(17)	-
Lymphocyte count decreased	7(39)	3(17)
Platelet Count decreased	7(39)	-
Electrolytes		
Hypophosphatemia	11(61)	4(22)
Hypomagnesemia	6(33)	-
Hyponatremia	6(33)	2(11)
Hypocalcemia	7(39)	1(5)
Hypokalemia	5(28)	-
Renal		
Proteinuria	6(33)	-
Hepatic		
ALT increased	10(61)	2(11)
AST increased	8(44)	1(5)
Hypoalbuminemia	5(28)	-
Pancreatic		
Amylase increased	4(22)	1(5)
Lipase increased	8(44)	4(22)
Endocrine		
Hypothyroidism	8(44)	-
Hyperthyroidism	2(11)	-

4.0 STUDY OBJECTIVES AND ENDPOINTS

Primary Objective	Primary Endpoint
To determine PFS for nivolumab/ipilimumab plus cabozantinib in patients with unresectable advanced melanoma	To determine the 1 year PFS rate for nivolumab/ipilimumab plus cabozantinib in patients with unresectable advanced melanoma using imRECIST
Secondary Objectives	Secondary Endpoints
To determine the response rate of nivolumab/ipilimumab plus cabozantinib in patients with unresectable advanced melanoma	To determine the ORR by imRECIST of nivolumab/ipilimumab plus cabozantinib in patients with unresectable advanced melanoma
To determine the OS of patients with unresectable advanced melanoma treated with nivolumab/ipilimumab plus cabozantinib	To determine the median and 3 year OS rate of patients with unresectable advanced melanoma treated with nivolumab/ipilimumab plus cabozantinib
To determine the safety profile of nivolumab/ipilimumab plus cabozantinib in	To determine the rate of all grade and grade 3-5 adverse events (treatment emergent and treatment related)

[figure not shown]
patients with unresectable advanced melanoma	
To determine the tolerability of nivolumab/ipilimumab plus cabozantinib in patients with unresectable advanced melanoma	To determine the rate of discontinuation of study drug(s) due to adverse events
Exploratory Objectives	
To determine associations between baseline tumor mutational burden (TMB), angiogenesis pathways, and immunophenotyping with clinical activity of nivolumab/ipilimumab plus cabozantinib in patients with unresectable advanced melanoma	To analyze molecular profiles based on whole exome sequencing (WES), PD-L1 immunohistochemistry and RNAseq from baseline tumors and correlate to ORR, PFS, and OS in patients with unresectable advanced melanoma treated with nivolumab/ipilimumab plus cabozantinib
To determine associations between baseline mutations in genes regulating anti-tumor immunity with tumor immunophenotype and clinical activity of nivolumab/ipilimumab plus cabozantinib in patients with unresectable advanced melanoma	To determine if loss of critical immune genes (such as IFN receptor and MHC) are associated with a low IFN gamma gene expression profile and impact on baseline tumors and correlate to ORR, PFS, and OS in patients with unresectable advanced melanoma treated with nivolumab/ipilimumab plus cabozantinib
To assess on treatment biopsy for evidence of increased immune infiltration, vascularization, and MHC expression to nivolumab/ipilimumab plus cabozantinib in patients with unresectable advanced melanoma	To determine change in immune cell populations, CD31 vascularization, and MHC class I expression by multiplex immunofluorescence (IF) between baseline and on treatment tumor specimens

5.0 STUDY DESIGN

5.1 Overall Schema

Subjects with unresectable advanced melanoma meeting eligibility criteria (refer to Section 6.0) will be screened for participation on the protocol. The screening phase will include obtaining baseline imaging studies, labs, history & physical, EKG, and collection of a fresh tumor biopsy or archived tumor specimen (refer to Table 7-1). Once meeting eligibility criteria and enrolled on study, subjects will begin treatment with nivolumab/ipilimumab and cabozantinib starting on day 1 of cycle 1. The treatment schedule and follow up is outlined further in the schema Figure 5-1 and Table 7-1. Patients who attain confirmed response or stable disease and are able to tolerate study drugs will continue treatment for up to 2 years. Discontinuation after 1 year but prior to 2 years will be permitted at the discretion of the treating investigator in patients with disease control achieving either a complete or partial response.

Figure 5-1. Treatment Schema

5.2 Study Drug Dosing

Induction phase:

Nivolumab 3mg/kg IV plus Ipilimumab 1mg/kg IV every 3 weeks x 4 cycles (12 week period)

Cabozantinib 40mg PO daily for 12 weeks

When nivolumab and ipilimumab are to be administered on the same day during the induction phase, nivolumab is to be administered first over 30 minutes. Nivolumab infusion must be promptly followed by a saline flush to clear the line of nivolumab before starting the ipilimumab infusion. The second infusion will be the ipilimumab over 30 minutes and will start after the infusion line has been flushed, filters changed, and participant has been observed to ensure no infusion reaction has occurred. The time in between infusions is expected to be approximately 30 minutes but may be more or less depending on the situation. Infusion window of -5 minutes/+ 10 minutes for each study drug.

Cabozantinib is an oral tablet taken by the patient daily. Participant is to self administer at the same time every day +/- 1 hour window. Participant is not to eat for at least 2 hours before and at least 1 hour after taking the medication.

A window of ± 3 days may be applied to all study visits.

Maintenance phase:

Nivolumab 480mg IV every 4 weeks for up to 92 weeks

Cabozantinib 40mg PO daily for up to 92 weeks

Maintenance therapy will continue for up to 92 weeks to complete 2 years total of treatment if tolerating therapy well and disease is controlled.

Nivolumab is administered over a 30 minute infusion without any premedication unless there is a prior history of infusion reaction. Nivolumab infusion must be promptly followed by a saline flush to clear the line of nivolumab. Participant is to be observed following infusion to ensure no infusion reaction has occurred.

Cabozantinib is an oral tablet taken by the patient daily. Participant is to self administer at the same time every day +/- 1 hour window. Participant is not to eat for at least 2 hours before and at least 1 hour after taking the medication.

A window of ± 3 days may be applied to all study visits.

5.3 Biospecimen collection

Baseline tumor collection

Prior cycle 1 of study, all patients must have either an archived tumor specimen available or a fresh biopsy for confirmation of disease and correlative studies. Fresh tumor biopsies may be core needle, punch, or incisional/excisional biopsy. Patients without a safe site of biopsy (as assessed by treating provider) or archived specimen will be exempt from this requirement and may obtain a waiver from the principal investigator after discussion. **Refer to lab manual for specific details on handling, processing and storage.**

On treatment tumor collection

Fresh tumor collection at week 13 (refer to Table 7-1) will be optional in patients with a palpable superficial tumor in the skin, subcutaneous tissue or lymph node. This can be a core needle biopsy, punch biopsy, or incisional/excisional biopsy. Patients without a safe site of biopsy (as assessed by treating provider) will not be considered eligible for the optional biopsy. **Refer to lab manual for specific details on handling, processing and storage.**

At progression tumor collection

Fresh tumor collection at time of progression (refer to Table 7-1) will be optional. This can be a core needle biopsy, punch biopsy, or incisional/excisional biopsy. **Refer to lab manual for specific details on handling, processing and storage.**

Peripheral blood biospecimen collection

Blood samples for study of serum, peripheral blood mononuclear cells (PBMCs), and other components will be collected. Samples will be processed using standard protocols and stored at -

80 degrees Celsius for future analyses. **Refer to lab manual for specific details on handling, processing and storage.**

Stool biospecimen collection

Baseline stool samples will be collected from patients at the start of treatment. Patients will be given a stool kit (Omnigene®-Gut tube, and collection materials including a toilet hat and tool for stool transfer). Patients will need to provide the sample on day 1 of the first cycle (+/- 7 day window). **Refer to lab manual for specific details on handling, processing and storage.**

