- ii. Uncontrolled hypertension defined as sustained blood pressure (BP) > 150 mm Hg systolic or > 100 mm Hg diastolic despite optimal antihypertensive treatment.
 - iii. Stroke (including transient ischemic attack [TIA]), myocardial infarction (MI), or other ischemic event, or thromboembolic event (eg, deep venous thrombosis, pulmonary embolism) within 6 months before first dose.
 - b. Gastrointestinal (GI) disorders including those associated with a high risk of perforation or fistula formation:
 - i. The subject has evidence of tumor invading the GI tract, active peptic ulcer disease, inflammatory bowel disease (eg, Crohn's disease), diverticulitis, cholecystitis, symptomatic cholangitis or appendicitis, acute pancreatitis, acute obstruction of the pancreatic duct or common bile duct, or gastric outlet obstruction.
 - ii. Abdominal fistula, GI perforation, bowel obstruction, or intra-abdominal abscess within 6 months before first dose.
Note: Complete healing of an intra-abdominal abscess must be confirmed before first dose.
 - c. Clinically significant hematuria, hematemesis, or hemoptysis of > 0.5 teaspoon (2.5 ml) of red blood, or other history of significant bleeding (eg, pulmonary hemorrhage) within 12 weeks before first dose.
 - d. Cavitating pulmonary lesion(s) or known endotracheal or endobronchial disease manifestation.
 - e. Lesions invading or encasing any major blood vessels.
 - f. Other clinically significant disorders that would preclude safe study participation.
 - i. Serious non-healing wound/ulcer/bone fracture.
 - ii. Uncompensated/symptomatic hypothyroidism.
 - iii. Moderate to severe hepatic impairment (Child-Pugh B or C).
10. Major surgery (eg, GI surgery, removal or biopsy of brain metastasis) within 8 weeks before first dose of study treatment. Complete wound healing from major surgery must have occurred 1 month before first dose and from minor surgery (eg, simple excision, tooth extraction) at least 10 days before first dose. Subjects with clinically relevant ongoing complications from prior surgery are not eligible.
11. Corrected QT interval calculated by the Fridericia formula (QTcF) > 500 ms per electrocardiogram (ECG) within 28 days before first dose of study treatment [32].

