2. Labs for Day 1 of each Cycle Week include CBC^a, comprehensive metabolic panel^a, free T3, free T4, TSH, INR/PT, PTT, urinalysis, spot UPCR and Creatine Kinase (CK) with Troponin I if CK is abnormal. Labs for Day 8 of each Cycle Week include only liver

function tests (ALT, AST, alkaline phosphatase, GGT, total protein, albumin, and total bilirubin).

3. Only required for premenopausal female subjects. Urine or blood HCG.
4. CT scan of the chest, abdomen and pelvis. Tumor Imaging Assessments are to be performed within 4 weeks of Cycle 1 Day 1 for the Baseline Screening Assessment. Patients with primary or metastatic disease involving the head or neck areas will require CT scan of the neck as well. MRI brain will be performed at baseline and per discretion of the treating investigator during the treatment period. In patients with a history of a prior brain metastasis, MRI brain will be performed at each reassessment. In patients with active, untreated brain metastases, MRI of the brain should be performed every 6 weeks through week 25 on protocol. Brain imaging with CT scan with IV contrast can be performed in place of MRI brain if there is a contraindication for MRI.
5. Optional core needle biopsy or punch biopsy of superficial tumor in the skin, subcutaneous tissue or lymph node that is palpable on treatment and at progression.
6. Scans every 12 weeks. Scans should occur prior to the visit. A window of -7 to +3 days is acceptable.
7. Patients will need to provide the sample on day 1 of the first cycle (+/- 7 day window).
8. Research blood collection should occur based on the calendar whenever possible and are not required to be redrawn due to treatment delays or interruptions.
9. Follow up off treatment will continue for 2 years after treatment is discontinued. Beyond this time point, progression free survival and overall survival would be assessed every 6 months via chart review or phone contact.

ECG, electrocardiogram; ECOG, Eastern Cooperative Oncology Group; PT/INR, prothrombin time/International Normalized Ratio; PTT, partial prothrombin time; UPCR, urine protein/creatinine ratio

^aLaboratory tests should include a standard hematology panel (CBC, differential, platelets) and chemistry panel (albumin, alkaline phosphatase, ALT, amylase, AST, bicarbonate, bilirubin, blood urea nitrogen, calcium, chloride, creatinine, glucose, lactate dehydrogenase, lipase, magnesium, phosphorus, potassium, sodium, total protein)

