8.2 Investigational Treatment: Cabozantinib

Cabozantinib tablets are supplied as film coated tablets containing cabozantinib malate equivalent to 20 mg of cabozantinib and contain microcrystalline cellulose, lactose anhydrous, hydroxypropyl cellulose, croscarmellose sodium, colloidal silicon dioxide, magnesium stearate and Opadry® yellow. The 20-mg tablets are round. Doses of 40 mg will comprise two 20-mg tablets. The components of the tablets are listed in Table 8-1.

- Dose reductions or interruptions may also occur in the setting of lower grade toxicity than defined in Table 8-3, if the investigator feels it is in the interest of a subject’s safety and will optimize drug tolerability.
- Interruption of cabozantinib treatment for cabozantinib-related AEs may occur at any time per investigator discretion. If treatment is interrupted due to related AEs for more than 6 weeks, cabozantinib should be discontinued unless there is unequivocal evidence that the subject is benefitting. In this situation, a subject may be able to restart therapy with a dose reduction upon resolution of the toxicity per the discretion of the investigator.
- Dose interruptions for reason(s) other than related AEs (eg, surgical procedures) can be longer than 6 weeks per the discretion of the investigator.

Guidelines for the management of specific AEs are provided in Section 8.2.4.

Table 8-2: Dose Reductions of Cabozantinib

Assigned Dose	First Dose Level Reduction	Second Dose Level Reduction
40-mg cabozantinib oral qd qd, once daily	20-mg cabozantinib oral qd	No dose reduction permitted

Cabozantinib will be discontinued if a qd dose of 20-mg cabozantinib (minimum dose) is not tolerated

Table 8-3: Dose Modifications of Cabozantinib for Treatment-Related AEs

CTCAE v.4.0 Grade	Recommended Guidelines for Management^a
Grade 1 AEs	Add supportive care as indicated. Continue cabozantinib treatment at the current dose level if AE is manageable and tolerable.
Grade 2 AEs which are tolerable and are easily managed	Continue cabozantinib treatment at the current dose level with supportive care.
Grade 2 AEs which are intolerable and cannot be adequately managed	At the discretion of the investigator, cabozantinib should be dose reduced or interrupted. Note: It is recommended that dose holds be as brief as possible.

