8.2.4.1.7 Skin and Subcutaneous Tissue Disorders

Wound healing and surgery: Cabozantinib has the potential to cause wound healing complications and wound dehiscence which may even occur long after a wound has been considered healed. Therefore, surgical and traumatic wounds must not only be completely healed prior to starting cabozantinib treatment but must also be monitored for wound dehiscence, wound infection and other signs of impaired wound healing while the subject is being treated with cabozantinib. If dehiscence occurs, cabozantinib treatment should not be restarted until complete healing has taken place.

Treatment with cabozantinib should be stopped at least 28 days prior to scheduled surgery. The decision to resume treatment with cabozantinib after surgery should be based on clinical judgment of adequate wound healing.

Palmar-plantar erythrodysesthesia syndrome (PPES; also known as hand-foot syndrome), skin rash (including blister, erythematous rash, macular rash, skin exfoliation, dermatitis acneiform, and papular rash), pruritus, dry skin, erythema, pigmentary changes, and alopecia have been reported with cabozantinib. All subjects on study should be advised on prophylactic measures including the use of emollients, removal of calluses, avoidance of exposure of hands and feet to hot water leading to vasodilatation, protection of pressure-sensitive areas of hands and feet, and use of cotton gloves and socks to prevent injury and keep the palms and soles dry. Early manifestations include tingling, numbness, mild hyperkeratosis, and symmetrical red and swollen areas on the palms and soles. The lateral sides of the fingers or periungual zones may also be affected. Adequate interventions are required to prevent worsening of skin symptoms such as blisters, desquamations, ulcerations, or necrosis of affected areas. Analgesics may be required for pain control.

Aggressive management of symptoms is recommended, including early dermatology referral. Treatment recommendations in response to PPES are summarized in Table 8-6.

Table 8-6: Management of Hand-Foot Syndrome (PPES) Associated with Cabozantinib

CTCAE v.4.0 Grade	Action To Be Taken

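### Section 5.3 allows excisional biopsy at week 13 on daily cabozantinib, while Table 7-1 footnote 5 lists only core needle or punch: a minor safety and consistency fix

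*Combined protocol and SAP*

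**What the plan says.** **Biopsy method.** Section 5.3 (Biospecimen collection), on the optional week-13 sample from a palpable superficial lesion: "This can be a core needle biopsy, punch biopsy, or incisional/excisional biopsy. Patients without a safe site of biopsy". Its paragraph on the progression sample gives the same list of methods. Table 7-1 footnote 5 (Section 7.2) covers both biopsies and reads: "Optional core needle biopsy or punch biopsy of superficial tumor in the skin, subcutaneous tissue or lymph node". Footnote 1 of that table, for baseline tissue, does include incisional and excisional biopsy.

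**Dosing around week 13.** Section 5.2 gives cabozantinib 40 mg daily through the 12-week induction, then in maintenance "Cabozantinib 40mg PO daily for up to 92 weeks". Table 7-1 calls the dosing continuous and marks it at week 13. No section sets a hold for the biopsy.

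**Wounds and surgery.** Section 8.2.4.1.7: "Cabozantinib has the potential to cause wound healing complications and wound dehiscence which may even occur long after a wound has been considered healed". It adds: "Treatment with cabozantinib should be stopped at least 28 days prior to scheduled surgery". Exclusion criterion 10 (Section 6.0) requires complete wound healing "from minor surgery (eg, simple excision, tooth extraction) at least 10 days before first dose". Section 8.2 leaves surgical interruptions to the investigator: "Dose interruptions for reason(s) other than related AEs (eg, surgical procedures) can be longer than 6 weeks per the discretion of the investigator".

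**The concern.** Two current texts describe the same procedure differently, and they differ on the method that makes the larger wound. The drug being taken at the time is one that the protocol itself links to impaired wound healing. A site following Section 5.3 may excise; a site following the table's footnote would take a core or a punch.

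The general surgical rule does not settle the matter, because it never says whether an excisional research biopsy is scheduled surgery. Criterion 10 treats a simple excision as minor surgery that must have healed before the first dose. Section 5.3 lets a similar wound be made during dosing with no stated interval. What is at stake is an avoidable wound, or an avoidable loss of study drug, for an optional exploratory sample.

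**Working it through.** The plan states no figure on this point, so the check is a comparison of texts plus one piece of arithmetic.

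**Step 1: do the texts conflict?**
- Baseline tissue: Section 5.3 and footnote 1 both include excision. They agree.
- Week 13: Section 5.3 includes excision; footnote 5 lists core needle and punch. They differ.
- Progression: Section 5.3 includes excision; footnote 5 lists core needle and punch. They differ.

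The table therefore includes excision before drug and leaves it out afterwards, while Section 5.3 makes no such distinction.

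**Step 2: what if the 28-day stop applies to an excisional biopsy?**
- Inputs: induction is 12 weeks (Section 5.2), or 12 × 7 = 84 days. Week 13 day 1 is therefore day 85. The stop is at least 28 days (Section 8.2.4.1.7).
- Hold starts on day 85 − 28 = day 57 and runs through day 84.
- Share of induction cabozantinib lost: 28 / 84 = 33%.
- With the ±3-day visit window, a biopsy on day 88 would put the hold on days 60 to 87. Of these, 25 are induction days: 25 / 84 = 30%.

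The sample would also be taken with little cabozantinib on board. Section 3.4 says: "The predicted terminal half life of cabozantinib at the approved dose of 60mg daily in RCC patients was 99hrs". Assuming that figure carries over to 40 mg in melanoma, 28 days is 672 h, and 0.5^(672/99) = 0.9% of the drug remains. An assumed half-life of 80 to 120 h gives 0.3% to 2.1%. This describes drug level only, not how fast vascular or immune effects reverse. It still sits badly with an exploratory endpoint that compares vascularization and immune cells on treatment with baseline.

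**Step 3: what if the stop does not apply?** An excision wound is then made at 40 mg daily, with dosing continuing. The remaining safeguards are the provider's view that the site is safe, interruption at the investigator's discretion, and wound monitoring afterwards. None is a stated rule for this biopsy. Section 8.2.4.1.8 shows that the protocol can set a procedure-specific hold: it asks for at least 4 weeks off cabozantinib before unavoidable dental procedures. The rationale there is osteonecrosis, so this is an analogy and not a rule for biopsies.

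**Step 4: is either outcome necessary?** No. A core needle or punch biopsy satisfies both texts and avoids the excision wound.

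**The case against.** The case for leaving the text alone has weight. Footnote 5 lists two methods without saying that no other is allowed, and a site choosing either one complies with both texts. The biopsy is optional, needs a palpable lesion, and is closed to subjects without a safe site. Sites may interrupt dosing. Nothing suggests that a provider would impose a 28-day hold for a research excision when a core or punch is available. Criterion 10 governs eligibility, not procedures on treatment. All of this stands. It makes the point small, but does not remove the mismatch or say which text governs.

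A reader might infer two stronger conclusions.

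**That the protocol breaks its own surgical rule.** The documents do not support this, because the rule does not name biopsies and may not cover them.

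**That an excised target lesion would distort response rate or 1-year PFS.** Section 7.5 is silent on a removed target. If its absence were scored as 0 mm, removing an assumed 15 mm skin lesion from a 45 mm sum would leave 30 mm, a 33% fall that would look like a partial response. To reach a wrong 1-year PFS status, however, a subject must accept the biopsy, have a palpable target, have it removed whole despite footnote 5, be scored at 0 mm, and then grow within a narrow band at the critical time. Section 9.2 also points away from surgery on tumor lesions before progression, although it is worded for local anticancer treatment. Whether the cited imRECIST source covers a removed lesion cannot be checked here.

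Under the 8-of-14 and 16-of-23 success thresholds, one wrong status would change the trial's conclusion with probability 4%, 13% or 14% at true rates of 50%, 60% or 75%. With an assumed 5% to 20% chance of one such subject, that is 0.05 × 0.04 = 0.2% to 0.20 × 0.14 = 2.8% of trials. The 5% to 20% has no basis in the documents, and its upper end looks implausible given that chain.

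**Conclusion.** The concern holds as a minor safety and consistency point. Section 5.3 and footnote 5 disagree on biopsy method at week 13 and at progression, and the surgical rule leaves a research excision undefined. Read one way, 28 of 84 induction cabozantinib days (33%) are lost; read the other, an avoidable wound is made on full dose. The 33% rests on a biopsy at day 85 and the minimum 28-day stop.

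Few subjects are likely to be affected, though the documents give no figure for uptake of the optional biopsy. The sample size and decision rule are untouched. The effect of scoring an excised target on response rate or 1-year PFS is speculative and negligible, and does not support the change. The mismatch itself is certain; how often it would matter is not known.

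**What to change.** - In Section 5.3, limit the week-13 biopsy to core needle or punch, matching footnote 5.
- State there that a target lesion is not to be removed whole.
- In the same edit, bring the progression-biopsy wording into line with footnote 5: core needle or punch while the subject is still taking cabozantinib. If excision is to remain possible after cabozantinib has stopped, say so in both places.

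This takes a few lines of text and no extra procedures. The downside is that some optional samples will be smaller, and some will be forgone where only an excision would have been practical.
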